### **Tacrolimus**

Tacrolimus will be administered either orally in the capsule format or enterically with the liquid suspension for those who are unable to take oral medications at the time of transplant. Patients should remain throughout the study within the tacrolimus C-0h blood trough levels as pre-specified in the trial protocol. The tacrolimus dose should be adjusted if tacrolimus C-0h blood trough levels are outside the required drug target range. In case of severe tacrolimus toxicity, dose reductions below the target levels may be performed at the investigator's discretion. If tacrolimus is interrupted for more than 21 consecutive days or cumulative for more than 28 days, discontinuation of study medication should be considered. In particular, interruptions for an elective medical treatment (e.g. dental treatments) are not to be counted. Tacrolimus may be interrupted during antibody treatment of rejection episodes or elective surgery.

### **Mycophenolate mofetil**

MMF will be administered either orally in the capsule format or enterically with the liquid suspension for those who are unable to take oral medications at the time of transplant. Patients should be administered and remain on MMF per institutional protocol. Dosage adjustments will be made based upon clinical practice/standard of care (SOC). Specifically, in subject randomized to group 2 (delayed everolimus), mycophenolate will be minimized as clinically indicated

## **Basiliximab Preparation and Administration**

The 20mg dose of basiliximab will be given per labeled indication on day 0 and POD 4. It will be diluted in 50mL of sterile 0.9% sodium chloride and may be administered via central or peripheral line over 20 to 30 minutes

## **Rescue medication - Handling of acute rejection**

In all suspected acute rejection episodes, regardless of initiation of anti-rejection treatment, a graft core biopsy will be performed preferably within 24 hours, latest within 48 hours, if clinically possible. Whenever possible, anti-rejection therapy should be postponed until a histological diagnosis of rejection is confirmed.

Acute rejections will be treated with bolus methylprednisolone (other corticosteroids are acceptable at an equivalent dose) according to local practice.

Other anti-rejection therapies (i.e. antibody therapy) should only be used in cases of steroid resistant rejections, or severe rejections with rejection activity index  $\geq 7$ , or rare events of vascular rejection. A biopsy-proven acute rejection occurring  $> 14$  days after the last day of the course of antirejection therapy given for the previous episode will be counted as a distinct event.

## **Concomitant medications**

Investigator will be diligent and avoid administrating therapy with drugs that potentiate tacrolimus-related nephrotoxicity.

In particular, the use of the following treatments is NOT allowed:

- Other investigational drugs and non-protocol specified immunosuppressant drugs.
- Drugs or substances that are strong inhibitors or inducers of CYP3A4. Certain drugs may need to be used if no alternative treatment is available. In such cases, everolimus should be interrupted for the duration of the treatment.
- If clinically significant proteinuria or nephrotic range proteinuria (protein-to-creatinine ratio  $\geq 500$  mg/m2/24 hrs) occurs throughout the duration of the study, introduction of an angiotensin converting enzyme inhibitor or angiotensin receptor blocker should be considered as per local practice.

### **Cytomegalovirus (CMV) prophylaxis**

Cytomegalovirus (CMV) prophylaxis will be administered according to local practice.

### **Pneumocystis pneumonia (PJP) prophylaxis**

Prophylactic treatment for pneumocystis jiroveci pneumonia (PJP) consisting Bactrim® or equivalent (trimethoprim /sulfamethoxazole), starting when oral medication can be tolerated will be used as per local practice. Atovaquone or dapsone will be administered to patients unable to tolerate trimethoprim/sulfamethoxazole as per local practice.

### **Fungal Prophylaxis/Treatment**

All patients will receive fungal prophylaxis and treatment according to local standard of care. Use of moderate inhibitors such as fluconazole will be permitted.

If the systemic use of a strongly interacting drug is required, study medication can be temporarily interrupted (or permanently discontinued).

### **Hepatitis B (HBV) prophylaxis**

Prophylaxis for recurrent hepatitis B during the course of this study will be per institutional protocol.

### **Hepatitis C (HCV) treatment**

Treatment for HCV disease can be done but not preemptively. Investigators treat HCV only when recurrent HCV disease has been documented, based on histological evidence as determined by the local pathologist. Therapies used for post-baseline HCV disease will be appropriately documented.

### **Lipid lowering medications**

During the course of the study, the lipid profile will be monitored. Lipid lowering medications should be administered according to guidelines and local practice.

HMG CoA reductase inhibitors (e.g., pravastatin) will be administered according to local practice for the management of hyperlipidemia. Patients requiring treatment with this class of medication (especially lovastatin) should be monitored closely for signs of rhabdomyolysis, such as, dark-colored urine, fever, muscle cramps, pain, spasm, or stiffness, unusual tiredness or weakness. Lipid lowering therapy will be optimized before dosage reduction of study medication is considered.

### **Contraception**

There are no adequate data from the use of everolimus in pregnant women. Studies in animals have shown reproductive toxicity effects including embryotoxicity and fetotoxicity. The potential risk for humans is unknown. Everolimus did not show genotoxicity in *in vitro* tests for gene mutations (bacteria and mammalian cells), and in an *in vitro* test and an *in vivo* mouse micronucleus assay for clastogenic activity. Therefore, male contraception is not indicated.

### **Other concomitant medication**

Concomitant use of medications with a strong effect on CYP3A4 must be avoided, because of the risk for over- or under-exposure to everolimus. Investigators will instruct the subject to notify the study site about any new medications he/she takes after the start of the study medications.

### **Prohibited treatment**

Uses of immunosuppressive agents such as azathioprine, sirolimus, and induction therapy with ALG, ATG, alemtuzumab or anti-tuberculosis agent as rifampin, and growth hormone therapy will not be allowed throughout the study.

### **Discontinuation of study treatment and premature patient withdrawal**

#### **Study treatment discontinuation**

The investigators will discontinue study medication for a given patient or withdraw the patient from study if, on balance, he/she believes that continuation would be detrimental to the patient's well-being. In the absence of medical contraindication or significant protocol violation, every effort will be made to continue the patient on study medication

Reasons for study drug discontinuation include:

- Death.
- Graft loss and/or re-transplantation.
- Pregnancy
- Withdrawal of consent.
- Emergence of any serious adverse event (at the discretion of the investigator).
- Unsatisfactory therapeutic effect (e.g. repeated acute rejection).
- Administration of prohibited immunosuppressive medication.
- Abnormal laboratory value(s) not resolved after study treatment interruption for more than 21 consecutive days or more than 2 episodes longer than 10 days, everolimus C-0h blood trough level  $\geq 3$  ng/mL cannot be maintained due to toxicity.
- Abnormal test procedure result(s).
- Significant protocol violation.
- Any other protocol deviation that results in a significant risk to the patient's safety.
- Lost to follow-up.

## **Efficacy**

### **Liver biopsy for suspected acute rejection**

Liver biopsies will be performed in all cases of suspected acute rejection preferably within 24 hours and latest within 48 hours, whenever clinically possible. Whenever it is possible, anti-rejection therapy should be postponed until a local histological diagnosis of rejection is confirmed. The liver biopsy will be read by the pathologist according to the Banff classification of liver allograft rejection and will be used for patient management and treatment.

### **Acute rejection**

All clinical suspected acute rejection episodes will be documented with the histological and clinical diagnosis specified.

Treated acute rejection is defined as a clinically suspected acute rejection whether biopsy proven or not, which has been treated and confirmed by the investigator according to the response to therapy.

## **Biopsy proven acute rejection and treated biopsy proven acute rejection**

A biopsy proven acute rejection (BPAR) is defined as clinically suspected acute rejection confirmed by biopsy. In all suspected acute rejection episodes, regardless of initiation of anti-rejection treatment, a graft core biopsy will be performed preferably within 24 hours, latest within 48 hours whenever clinically possible. Whenever it is possible, anti-rejection therapy should be postponed until a local histological diagnosis of rejection is confirmed. The liver biopsies will be read by the pathologist according to the Banff classification of liver allograft rejection. The local histo-pathology results will be used for patient treatment and management. A treated biopsy proven acute rejection (tBPAR) will be considered as efficacy event if the local pathologist reading with a RAI score  $\geq 3$  of acute rejection index was applied and consecutive anti-rejection therapy was administered to the patient. These readings will be used to assess the efficacy endpoint at Months 3 and 5 after the start of everolimus based regimen.

## **Safety**

### **Renal function**

Serum creatinine, blood urea nitrogen, and serum cystatin C will be measured at all study visits and will be used to estimate the glomerular filtration rate by C/G (MDRD)

## **Statistical analysis**

TBD

## **Projected Enrollment Period**

March 22, 2019 through December 31, 2020

## **Patient Population**

In a 2:2:1 scheme, 90 patients will be randomized at UCLA Medical Center between March 22, 2019 through December 31, 2020. Each patient will be followed for six months post-transplant.

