# Study Synopsis

## TITLE

An single center, open label, randomized, prospective, phase 4 study of induction and maintenance immunosuppression in adult subjects age >18 years undergoing orthotopic liver transplantation (OLT) with basiliximab, delayed dose tacrolimus plus mycophenolate mofetil and standard of care (SOC) corticosteroids (Group 1) versus basiliximab, delayed dose tacrolimus plus mycophenolate mofetil, SOC corticosteroids, with addition of delayed maintenance everolimus at one month post OLT with subsequent mycophenolate mofetil minimization (Group 2) versus standard dose tacrolimus plus mycophenolate mofetil plus SOC corticosteroids (Group 3; control) with a high risk of developing renal dysfunction following OLT or with concomitant renal dysfunction prior to OLT.

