## **PATIENT POPULATION**

In a 2:2:1 fashion, 90 subjects (group 1: n=36; group 2: n=36; group 3: n=18) will be randomized at UCLA Medical Center. Each subject will be followed for 6 months post-transplant.

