## **Purpose**

### Primary Objectives

- To evaluate the evolution of renal function assessed by dialysis independence and time to independence from dialysis.

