## **Inclusion Criteria at Baseline**

Patients eligible for inclusion in this study have to fulfill all of the following criteria:

1. A signed informed consent prior to patient participation in the study and before any assessment is performed.
2. Patients who are able to take oral medication at 1 month post transplant

3.  $\geq 18$  years old
4. Undergoing first OLT
5. Dialysis for 45 days or less at time of transplant
6. Able and willing to conform to requirements of the study
7. Able and willing to provide informed consent or have legally authorized representative who is able and willing to provide informed consent

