## **Exclusion Criteria**

1.  $< 18$  years old
2. Autoimmune liver disease, Primary Sclerosing Cholangitis, Primary Biliary Cirrhosis
3. Dialysis greater than 45 days
4. Receiving ATG, IVIG therapy, or sirolimus/everolimus around time of transplant or sirolimus/everolimus after transplant
5. Unable to take oral medications at 1 month post transplant
6. Participating in another clinical research study involving the evaluation of another investigational drug or device
7. Documented allergy to basiliximab, TAC, MMF or any macrolide antibiotic.
8. Presence of thrombosis of any major hepatic arteries
9. Complex/high risk arterial reconstruction at any time (graft vessel patency by Doppler ultrasound confirmed and documented).
10. Patients who are recipients of multiple solid organ transplants, (e.g., multivisceral or combined liver-kidney transplants), or have previously received an organ or tissue transplanted, or who received an ABO incompatible transplant.
11. Patients who have severe hypercholesterolemia ( $>215$  mg/dL;  $>5.5$  mmol/L) or hypertriglyceridemia ( $>265$  mg/dL;  $>3.0$  mmol/L) at Baseline.
12. Patients who have severe thrombocytopenia or neutropenia (platelet count  $>20$  and MLCs $>1000$ )
13. Patients who have any surgical or medical condition, which in the opinion of the investigator, might significantly alter the absorption, distribution, metabolism and excretion of study drugs
14. Patients with a known hypersensitivity to the drugs used on study or their class, or to any of the excipients.
15. Patients with clinically significant systemic infection
16. Pregnant or nursing (lactating) female patients, where pregnancy is defined as the state of a female after conception and until the termination of gestation, confirmed by a positive  $\beta$ HCG laboratory test ( $>9$  mIU/mL) at Baseline.

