Official Title:

A Study in Adults on Pre-LT Dialysis With Basiliximab, Delayed Tacrolimus (TAC), Mycophenolate (MMF), and Steroids (Group 1) vs. Basiliximab, Delayed TAC, MMF, Steroids, With Everolimus 30 Days Post-LT (Group 2) vs. TAC, MMF, and Steroids (Group 3)

NCT Number:

NCT04104438

Document Date:

September 3, 2020

Statistical Analysis

Continuous variables were expressed as median (range) and were compared using the Mann-Whitney U test. Categorical variables were expressed as a numerical percentage and compared by the Chi-square test or the Fishers Exact Test. Survival curves were generated by the Kaplan-Meier method, and differences in survival rates were analyzed using the Log-Rank test. All tests were two-sided, and the significance level was $p<0.05$. All analyses were performed using IBM® SPSS® Statistics version 26 (IBM Corporation, Armonk, NY).

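### The 2:2:1 randomisation names no stratification by dialysis at transplant and the SAP tests are unadjusted, so chance imbalance against the 18-patient control arm is left unhandled on a primary objective defined by dialysis

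*Protocol*

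**What the plan says.** **Allocation.** The protocol's Patient Population section states "In a 2:2:1 scheme, 90 patients will be randomized at UCLA Medical Center", and the synopsis gives the arm sizes as "group 1: n=36; group 2: n=36; group 3: n=18". The Study Population section repeats the 2:2:1 ratio. None of these places names a stratification factor, blocking, minimisation or a method of generating the list. The protocol's Statistical analysis section is still to be written.

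**Who is eligible.** Inclusion criterion 5 reads "Dialysis for 45 days or less at time of transplant" and exclusion criterion 3 reads "Dialysis greater than 45 days". Both set the same upper limit and neither sets a lower one. The protocol title describes patients "with a high risk of developing renal dysfunction following OLT or with concomitant renal dysfunction prior to OLT", which does not require dialysis. The SAP title differs: "A Study in Adults on Pre-LT Dialysis With Basiliximab".

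**What is measured.** The primary objective is "To evaluate the evolution of renal function assessed by dialysis independence and time to independence from dialysis". Creatinine, eGFR and dialysis requirement are secondary endpoints.

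**How it is analysed.** The SAP names the Mann-Whitney test, the chi-square or Fisher test, Kaplan-Meier curves and the log-rank test, two-sided at 0.05. It names no covariate, stratified test or regression model.

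**The concern.** Dialysis at transplant is the baseline factor closest to the primary objective, because a patient who is not on dialysis starts from the state that the others are trying to reach. It can also be expected to bear on early creatinine and eGFR. The protocol's own Introduction cites pre-transplant renal dysfunction as an independent predictor of postoperative mortality.

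Both comparisons with control depend on the same 18 patients, so each control patient carries 5.6 points of that arm's dialysed share (1/18). Neither the allocation nor the analysis, as specified, deals with the factor. At stake is the readability of the renal contrasts: a visible baseline gap on dialysis would leave the result open to argument, with no prespecified analysis to settle it.

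**Working it through.** **The plan's own figure.** 90 × 2/5 = 36, 90 × 2/5 = 36 and 90 × 1/5 = 18. The stated arm sizes reproduce. The total of 90 cannot be checked, since no power, effect size or event rate is given.

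**Inputs.** Arm sizes 36, 36 and 18 come from the protocol. The share on dialysis at transplant is not in the documents; it is assumed at 20, 30, 50, 70 and 80% of the 90, that is 18, 27, 45, 63 and 72 patients.

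**Spread of the gap between control and one experimental arm.** For a random split of a fixed group of 90 with dialysed share p, the standard deviation of the difference in dialysed share is √[p(1−p)(1/18 + 1/36) × 90/89].

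- p = 0.2 or 0.8: √(0.16 × 0.0833 × 1.0112) = 11.6 points
- p = 0.3 or 0.7: √(0.21 × 0.0833 × 1.0112) = 13.3 points
- p = 0.5: √(0.25 × 0.0833 × 1.0112) = 14.5 points; the same formula with 1/36 + 1/36 gives 11.9 points for the two experimental arms against each other

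**Chance of a gap.** The number dialysed in control is hypergeometric (18 drawn from 90). Given that, the number in Group 1 is hypergeometric (36 drawn from the remaining 72), and Group 2 takes the rest. Summing the exact probabilities:

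| Dialysed share (assumed) | ≥10 points, at least one control contrast | ≥15 points, at least one | ≥20 points, at least one | ≥20 points, one named contrast |
|---|---|---|---|---|
| 20% or 80% | 60% | 29% | 12% | 7% |
| 30% or 70% | 68% | 38% | 19% | 12% |
| 50% | 68% | 44% | 25% | 15% |

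**If every patient is dialysed.** The yes/no gap is then zero and only duration can be unbalanced. On a normal approximation, the standardised mean difference between control and one experimental arm has standard deviation √(1/18 + 1/36) = 0.289. The chance that it exceeds 0.25 is 39% for one contrast and 56% for at least one of the two. The chance that it exceeds 0.5 is 8% and 14%.

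**What a gap could do to a result (illustration only).** Assume dialysis at 6 months in 40% of those dialysed at transplant and 5% of the rest. A 20-point gap then shifts the comparison by 0.20 × (0.40 − 0.05) = 7 points. With half the patients dialysed, the overall rate is 0.5 × 0.40 + 0.5 × 0.05 = 22.5%, and the standard error of an 18 v 36 difference is √[0.225 × 0.775 × (1/18 + 1/36)] = 12 points. The shift is about 7/12 = 0.6 of a standard error.

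**Effect of stratifying.** In simulated permuted blocks of five (2:2:1, block size assumed) within two dialysis strata, the largest gap between control and an experimental arm was 5.6 points. No simulated allocation reached 10 points.

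**The case against.** **The population may be all dialysed.** Inclusion criterion 5 can be read as requiring dialysis, the SAP title says so, and an objective of becoming independent of dialysis fits that reading. The table above would then not apply. This stands as a condition on the figures: the documents conflict, and the protocol title supports a mixed population. Duration would still be uncontrolled.

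**Silence is not a decision.** A reader might infer that the trial is unstratified by design. The documents do not support that: they describe no allocation method at all, so the supportable statement is that no stratification is specified.

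**Randomisation already protects the comparison.** A reader might infer that the contrasts are biased, or that an imbalance could not be told apart from a treatment effect. Neither follows. Randomisation is unbiased on average and the tests' error rates allow for chance imbalance. The illustrated shift lies well inside sampling error. Dialysis history must be established to apply criterion 5, so an imbalance can be seen and adjusted for.

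**Dialysis at transplant does not fix the outcome.** A reader might also infer that baseline status decides whether dialysis independence can occur at all. The protocol counts dialysis requirements and renal replacement therapy after transplant, so a patient not dialysed at baseline may start dialysis and later come off it. If time to independence is analysed only among those on dialysis, an unequal share mainly costs precision.

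**It is a pilot.** The synopsis calls the study a single-centre pilot, so leaving out stratification is not an error in itself. That is fair, and it makes this an improvement rather than a correction. The SAP nevertheless tests at the 0.05 level, so the comparisons will be read as comparisons.

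**Conclusion.** The point holds as a worthwhile and inexpensive improvement. No stratification factor is specified and no adjusted analysis is planned, although the primary objective is defined on dialysis and no minimum dialysis exposure is required.

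Imbalances of 10 to 15 points against at least one experimental arm would be common. Gaps of 20 points or more would be a minority outcome, and less frequent still for any one named contrast. These sizes rest on a mixed population and on assumed dialysed shares. If all patients are dialysed, the exposure is limited to imbalance in duration. In either case the harm is loss of precision and of credibility in one small trial.

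**What to change.** 1. **Reconcile the population.** State whether dialysis at transplant is required, and bring the protocol title, inclusion criterion 5 and the SAP title into agreement.
2. **Stratify the remaining randomisation.** If the population is mixed, add to the protocol's population sections: *Randomisation is stratified by dialysis at transplant (yes/no), in permuted blocks that keep 2:2:1 within each stratum.* If all patients are dialysed, stratify by days of dialysis at a cut-point fixed in advance. With 18 controls, keep to this single factor.
3. **Match the analysis.** In the SAP, account for the same factor for all randomised patients: a stratified log-rank test for time to dialysis independence, and a stratified or baseline-adjusted comparison for dialysis status, creatinine and eGFR. This step matters most for patients already randomised. Enrolment was planned from March 2019 to December 2020 and the SAP is dated September 2020, so a change to allocation may reach few of them. Stratified allocation followed by unadjusted tests would also give up much of the precision gained.

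**Cost.** Two allocation lists instead of one at a single centre, final arm sizes possibly a patient or two away from 36:36:18 because of incomplete last blocks, and slightly more analysis work. The yes/no factor needs no new data.
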